#### **4.1 Subject Selection**

#### **4.2 Inclusion Criteria**

Subjects must meet all of the following inclusion criteria to be eligible for enrollment:

4.2.1 Patients must have a confirmed *TET2* mutations identified by next generation targeted deep sequencing.

4.2.2 Patients must have MDS, or MDS/MPN overlap defined by 2016 WHO criteria. Both newly diagnosed or previously treated MDS or MDS/MPN patients are eligible as long as the patient has never received prior treatment with azacitidine or decitabine.

4.2.3 Patients with Leukemic/blast phase transformation MPN.

4.2.4 Patient with AML according to 2016 WHO criteria (excluding APL [AML-M3]).

4.2.4.1 Newly diagnosed patients who are ineligible or declined to receive intensive chemotherapy after discussion of risks and benefits of that approach or patients with primary refractory/relapsed AML.

4.2.4.2 Patients with active central nervous system (CNS) leukemia eligible at the discretion of treating physician.

4.2.4.3 Relapse/Refractory is defined as at least 1 course of treatment for AML excluding any patients treated with azacitidine or decitabine.

4.2.4.3.1 Patients should be off any prior treatment or line of therapy for 2 weeks prior to start study with the exception of hydrea (Hydroxyurea).

4.2.5 Prior therapy with hydroxyurea, biological or targeted therapy (e.g. flt3 inhibitors, other kinase inhibitors) or hematopoietic growth factors is allowed.

4.2.6 Age  $\geq 18$  years.

4.2.7 ECOG performance status  $\leq 3$ .

4.2.8 Patients must have normal organ and marrow function as defined at the discretion of the treating physician and PI.

- 4.2.9 Women of childbearing potential must have a negative serum or urine pregnancy test within 10-14 days prior to enrollment.
- 4.2.10 Patients must have the ability to understand and the willingness to sign a written informed consent document.
- 4.2.11 Patient must be willing to comply with all aspects of the protocol including completing the drug diary.
- 4.2.12 Patient must discontinue any and all use of multivitamin and/or vitamin c medication 24 hours before first dose of Ascorbic Acid.

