### 8.1.2 Ascorbic Acid

### **COMMON, SOME MAY BE SERIOUS**

In 100 people receiving ascorbic acid more than 20 and up to 100 may have:

- Fatigue
- Headache
- Nausea
- Vomiting
- Diarrhea
- Constipation
- Loss of appetite
- Bruising
- Low blood cell counts
- Weakness
- Joint pain
- Shivering
- Cough
- Difficulty Breathing

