### **8.2.3 Adverse Event Evaluation**

The investigator or designee is responsible for ensuring that all adverse events (both serious and non-serious) observed by the clinical team or reported by the subject, which occur after the

subject has signed the informed consent are fully recorded in the subject's medical records. Source documentation must be available to support all adverse events.

The investigator or sub-investigator (treating physician if applicable) or delegated staff will provide the following for all adverse events (both serious and non-serious):

- Event term (as per CTCAE 4.1)
- Description of the event
- Date of onset and resolution
- **Expectedness of the toxicity**
- **Grade of toxicity**
- **Attribution of relatedness to the investigational agent- (this must be assigned by an investigator, sub-investigator, or treating physician)**
- Action taken as a result of the event, including but not limited to; no changes, dose interrupted, reduced, discontinued, etc. or action taken with regard to the event, i.e. no action, received conmed or other intervention, etc.
- Outcome of event

**An expected adverse event** is an event previously known or anticipated to result from participation in the research study or any underlying disease, disorder, or condition of the subject. The event is usually listed in the Investigator Brochure, consent form or research protocol.

**An unexpected adverse event** is an adverse event not previously known or anticipated to result from the research study or any underlying disease, disorder, or condition of the subject.

**Attribution** is the relationship between an adverse event or serious adverse event and the study drug. Attribution of any adverse event can only be assessed by the PI and/or Co-I. Attribution will be assigned as follows:

- Definite – The AE is clearly related to the study drug.
- Probable – The AE is likely related to the study drug.
- Possible – The AE may be related to the study drug.
- Unlikely – The AE is doubtfully related to the study drug.
- Unrelated – The AE is clearly NOT related to the study drug.

Protocol must specify if attribution is required for individual components of the treatment regimen or the treatment regimen as a whole.

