### **Definitions:**

#### **Responses for MDS patients:**

**Complete Response (CR):** Bone marrow:  $\leq 5\%$  myeloblasts with normal maturation of all cell lines; persistent dysplasia will be noted. Peripheral blood:  $\text{Hgb} \geq 11 \text{ g/dL}$   $\text{Platelets} \geq 100 \times 10^9 / \text{L}$   $\text{Neutrophils} \geq 1.0 \times 10^9 / \text{L}$ ,  $\text{Blasts} 0\%$

**Partial response (PR):** All CR criteria if abnormal before treatment except: bone marrow blasts decreased by  $\geq 50\%$  over pretreatment but still  $> 5\%$

**Marrow CR:** Blasts  $\leq 5\%$  and decrease by  $\geq 50\%$  from baseline (baseline blasts should be above 5% to be eligible for marrow CR)

**Hematologic Improvement (HI):** (responses must last at least 8 weeks) **Erythroid response** [HI-E; (if pretreatment  $\text{Hgb} < 11 \text{ g/dL}$ )]:  $\text{Hgb}$  increase by  $\geq 1.5 \text{ g/dL}$ ; Relevant reduction of units of RBC transfusions by an absolute number of at least 4 RBC transfusions/8 weeks compared with the pretreatment transfusion number in the previous 8 weeks. Only RBC transfusions given for an  $\text{Hgb}$  of  $\leq 9.0 \text{ g/dL}$  pretreatment will count in the RBC transfusion response evaluation.

**Platelet response** [HI-P; ((if pretreatment Platelet count  $< 100 \times 10^9 / \text{L}$ )]: Absolute increase of  $\geq 30 \times 10^9 / \text{L}$  for patients starting with  $> 20 \times 10^9 / \text{L}$  platelets, or increase from  $< 20 \times 10^9 / \text{L}$  to  $> 20 \times 10^9 / \text{L}$  and by at least 100%.

**Neutrophil response** [HI-N; (pretreatment,  $\text{ANC} < 1.0 \times 10^9 / \text{L}$ )]: At least 100% increase and an absolute increase  $> 0.5 \times 10^9 / \text{L}$

**Progression/Relapse after hematological improvement:**  $\geq 1$  of the following:  $\geq 50\%$  decrement from maximum response levels in granulocytes or platelets;  $\downarrow$  in Hgb by  $\geq 1.5$  g/dL; transfusion dependence

**Stable Disease:** Not satisfying criteria for Complete Remission, Partial Response, Marrow CR, Hematologic Improvement or Progression/Relapse.

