**Definition of secondary outcomes/endpoints:**

1. Incidence of adverse events of the combination defined by CTCAE 4.1 criteria.  
Toxicity will be any drug related Grade 3 or 4 toxicity.
2. Response duration to the combination recorded from start of treatment to progression
3. Overall survival measured from start of treatment to death or last follow up

**Sample size justification and study design:** The study sample size was determined using Minimax Simon's two-stage design (Simon, 1989. The null hypothesis that the true response rate is 0.3 will be tested against a one-sided alternative that the true response rate is 0.5. In the first stage, 12 patients will be accrued. If there are 3 or fewer responses, the study will be stopped. Otherwise, 16 additional patients will be accrued for a total of 28. The null hypothesis will be

rejected if 11 or more responses are observed in 28 patients. This design yields a type I error rate of 0.1 and a power of 0.8 when the true response rate is 0.5.

**Analysis plan:** Descriptive statistics will be used for the primary endpoint and secondary endpoints 1,2, and 3. Overall survival will be estimated with Kaplan Meier method and will be compared to the survival of a historical cohort of MDS patients treated at our institution with single agent Azacitidine between 2006-2012 using a one-sample log rank test. A Cochran-Mantel-Haenszel test will be used to test for differences in response rate by mutational status controlling for treatment. Unadjusted and adjusted logistic regression models were used to predict response to therapy. Models will be adjusted for covariates including age, sex, and other prognostic factors. The odds ratio (OR) and 95% confidence intervals (CI) will be estimated for the risk group (mutated) and compared with the reference group (WT).

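### Minor: the Grade 3/4 toxicity rate in secondary endpoint 1 ignores the entry grade, so for neutrophils and platelets it does not separate worsening on treatment from cytopenia already present

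*Combined protocol and SAP*

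**What the plan says.** Section 14.0 defines secondary endpoint 1 in two parts. The first is "Incidence of adverse events of the combination defined by CTCAE 4.1 criteria". The second narrows it: "Toxicity will be any drug related Grade 3 or 4 toxicity". Neither part mentions the grade before treatment, and the analysis plan for this endpoint is descriptive statistics only.

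Section 8.2.3 lists what is recorded for each event: term, description, dates, expectedness, grade, attribution, action and outcome. Entry grade is not on the list. Attribution is a physician's judgment on a five-level scale: "Attribution of any adverse event can only be assessed by the PI and/or Co-I".

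On who may enter, item 4.2.8 of the inclusion criteria says "Patients must have normal organ and marrow function as defined at the discretion of the treating physician and PI". No neutrophil or platelet minimum is given. The MDS response criteria in Section 12.0 score a neutrophil response when the pretreatment ANC is below 1.0 x10^9/L ("At least 100% increase and an absolute increase", with a stated minimum rise). They score a platelet response from starting counts below 100 x10^9/L, including counts below 20 ("HI-P; ((if pretreatment Platelet count" opens that rule).

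**The concern.** The first secondary objective (Section 2.2) is the safety profile of the combination. Section 1.1 describes MDS as a disease of cytopenias, and Section 1.2 names leukopenia and thrombocytopenia as common azacitidine effects. Disease and drug therefore lower the same counts. Section 7.0 also has cycle 2 given whatever the degree of myelosuppression.

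In a single-arm trial, a reader of the Grade 3/4 rate will want to know how much of the neutropenia and thrombocytopenia appeared or deepened on treatment. The planned rate cannot show that. A patient who enters at Grade 3 and stays there, and one who falls from a normal count to Grade 3, add the same one event if both are called drug related.

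**Working it through.** The documents give no toxicity rate, so there is no figure to reproduce. The check is a reading of the text, followed by the precision cost of the proposed addition.

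**1. Does a baseline condition appear anywhere else?** Baseline is mentioned in three other rules:
- Section 6.4, Table 1: when toxicity that fails to recover ends treatment.
- Section 7.0: when the next cycle may start.
- Section 8.4: how long related events are followed.

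None of them defines what counts as toxicity in Section 14.

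**2. Can patients enter at Grade 3 or 4?** CTCAE limits are not in the documents. Assumed, x10^9/L: ANC below 1.0 is Grade 3 and below 0.5 Grade 4; platelets below 50 are Grade 3 and below 25 Grade 4.
- Platelets below 20 at entry are Grade 4 for any Grade 4 limit of 20 or more.
- Every ANC below 1.0 at entry is Grade 3 or worse only if the Grade 3 limit is 1.0 or more. With a lower limit, only some of these patients are.
- No claim is made for hemoglobin. The documents do not show Grade 3 anemia at entry.

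The response criteria show what can be scored, not how many such patients enrol.

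**3. What does each measure count?** For one lineage:

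| Entry grade | Worst grade on treatment | Called drug related | Section 14 toxicity | At least one grade worse, Grade 3/4 |
|---|---|---|---|---|
| 0 | 3 | yes | counted | counted |
| 3 | 3 | yes | counted | not counted |
| 3 | 3 | no | not counted | not counted |
| 3 | 4 | yes | counted | counted |
| 3 | 4 | no | not counted | counted |
| 4 | 4 | yes | counted | separate row |

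The planned rate gives the first, second, fourth and sixth rows the same weight. The baseline-referenced measure tells them apart.

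**4. Are the data there?** Hematology is taken at screening (Section 11.1.1, item 3). On treatment it is taken on day 1 of each cycle and at C6D28 (Section 11.1, Treatment Period, item 1). Appendix VI includes neutrophils, platelets and hemoglobin. Transfusions and growth factors are documented before each cycle in the treatment period.

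**5. What does the addition cost in precision?** Patients at Grade 4 at entry cannot worsen by a grade, so they leave the at-risk denominator. Exact (Clopper-Pearson) 95% limits for x of n are the 0.025 quantile of Beta(x, n-x+1) and the 0.975 quantile of Beta(x+1, n-x). Half-width is (upper - lower)/2. At a 50% rate:

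| At Grade 4 at entry (assumed) | x/n | 95% CI | Half-width |
|---|---|---|---|
| 0 of 28 | 14/28 | 0.306-0.694 | 0.194 |
| 2 of 28 | 13/26 | 0.299-0.701 | 0.201 |
| 4 of 28 | 12/24 | 0.291-0.709 | 0.209 |
| 6 of 28 | 11/22 | 0.282-0.718 | 0.218 |
| 8 of 28 | 10/20 | 0.272-0.728 | 0.228 |
| 0 of 12 (stage 1 stop) | 6/12 | 0.211-0.789 | 0.289 |
| 2 of 12 (stage 1 stop) | 5/10 | 0.187-0.813 | 0.313 |

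The loss is about 1 to 3 points at 28 patients (0.201 - 0.194 = 0.007; 0.228 - 0.194 = 0.034) and about 2 points at 12 (0.313 - 0.289 = 0.024). These figures price the fix. They say nothing about the size of the problem.

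**The case against.** The best defense is that attribution is the plan's chosen way to separate drug from disease, and that physician judgment is common in single-arm trials. The recording rules help. Each event needs an onset date (Section 8.2.3), and safety reporting covers events that occur during treatment and for 30 days after (Section 8.4), so some unchanged entry cytopenias would not be counted. All events after consent are to be recorded, so the log may hold some information from before dosing. Item 4.2.8, read literally, asks for normal marrow function. And the shift table could be made at reporting without any plan text.

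Most of this stands as a limit on the point. It does not close it. The timing rules do not settle counts that fluctuate around, or worsen from, a severe entry value. Item 4.2.8 leaves its own definition to discretion, and the response criteria provide for cytopenic patients. Nothing commits the trial to the table.

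Three stronger readings are tempting, and the documents do not support them:
- *Low entry counts are what makes the rate depend on attribution.* Any drug-related rate does, whatever the baseline. Low counts only make the judgment harder.
- *The rate will be inflated by a large amount.* A figure would need the share of patients entering at Grade 3 or 4 and the share attributed to drug. The documents give neither, and assuming that every entry cytopenia is attributed runs against the timing rules.
- *The trial's safety decisions are affected.* The endpoint is descriptive, and the two-stage rule uses response only.

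**Conclusion.** The omission is real and minor. For neutrophils and platelets, the attributed Grade 3/4 rate does not separate worsening on treatment from cytopenia present at entry. Its size is unknown. The overall adverse event incidence in the same endpoint is not attribution-dependent. No trial-level test, threshold or stopping rule changes.

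The conclusion rests on the text of Section 14 and on patients being able to enter with Grade 3 or 4 counts, which in turn uses the assumed CTCAE limits. Two neighboring gaps are separate clarifications and carry no weight here: which attribution levels count as drug related, and whether attribution is to each agent or to the regimen. A baseline rule would cure neither.

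**What to change.** Keep the attributed Grade 3/4 rate for all events. Add to Section 14, for neutrophils, platelets and hemoglobin:
- baseline-to-worst-grade shift tables, with baseline as the last value before the first study drug dose (Day -3);
- the rate of post-baseline Grade 3 or 4 values at least one grade worse than baseline, regardless of attribution;
- grading from all available hematology values, including unscheduled ones, together with the grades in the adverse event log. Scheduled counts alone could miss mid-cycle nadirs;
- patients at Grade 4 at entry in a separate row, outside the at-risk denominator but visible;
- transfusion and growth-factor use alongside, since both can mask worsening.

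Use Day -3 to C6D28 as the main window and show cycles 7 onward separately, because Section 11.1 lists growth-factor documentation for the treatment period but not for the extended period.

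The cost is one paragraph and three tables, with no new tests or visits. The price is the smaller lineage denominators shown above. The addition still cannot fully separate drug effect from disease progression, and unsampled nadirs stay unseen. The plan should state both limits.

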### **2.2      Secondary Objective(s)**

To evaluate the following:

1. The safety profile of the combination of azacitidine and ascorbic acid in the targeted patient population.
2. The response duration for study patients.
3. The overall survival of the treated population (compared to matched historical cohort of patients treated with single agent Azacitidine)
4. The identification of genomic biomarkers that may predict response to the combination treatment.

5. Evaluation of changes in methylation prior and during therapy

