#### **3.2 Expected Duration of Treatment and Subject Participation**

Upon signing consent, patients will be enrolled onto the study. Patients will undergo a screening period. The screening period is defined as the time period between the signing of the consent to the day the patient receives the first dose of study drug. During this period the patient will be assessed to determine if the patient meets all inclusion and exclusion criteria to be eligible for the study (Appendix IV).

The treatment period is defined as the time between first day of study drug dosage (Day - 3) to C6D28. At this time the patient will be assessed and eligible to move into the Extended Treatment Period (ETP). The extended treatment period is defined as C7D1 to the patient meets EOT criteria (Section 6: Table 1; Appendix IV)

Study treatment is defined as the treatment period and if applicable the extended treatment period (Appendix IV). Study drug will be continued during the duration of the study treatment unless patients exhibit any EOT criteria (Section 6: Table 1; Appendix IV).

Treatment should be continued for at least 6 cycles in the absence of toxicities that require discontinuation and/or any EOT criteria (Section 6: Table 1; Appendix IV). After 6 cycles of treatment, a bone marrow biopsy and aspiration will be obtained to evaluate response. If patient has achieved either of the below response criteria (Appendix IV) based on their disease diagnosis patient will be eligible continue onto the extended treatment period (ETP). The patient is eligible to remain on treatment during the ETP until disease progression or patient meets EOT criteria (Section 6: Table 1; Appendix IV).

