#### **6.4 Criteria for Removal from Study Treatment (EOT)**

In the absence of treatment delays due to adverse events, treatment may continue for 6 cycles or be extended after 6 cycles unless 1 one of the following criteria applies:

End of Treatment Criteria

• Disease progression defined as no response after 6 months of treatment or loss of response during treatment as defined in section 12

• Intercurrent illness that prevents further administration of treatment

• The investigator and/or treating physician considers it to be in the best interest of the subject to permanently discontinue study treatment

○ This includes if the treatment is deemed to be of excessive toxicity to the patient by the treating physician

• Patient decision to withdraw from treatment (partial consent) or from the study (full consent)

• Pregnancy during the course of the study for a child-bearing participant

• Death

• Unacceptable adverse events defined as following:

○ Unacceptable treatment related toxicity, NCI CTC AE version 4.0 Grade 3 or 4 that fails to recover to baseline or < Grade 3 in the absence of treatment within 4 weeks

○ Any toxicity or other issue that causes a delay of study drug administration by more than 4 weeks

Table 1: End of Treatment Criteria

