#### **Treatment Period (Day -3 to C6D28)**

1. Hematology exams (Appendix VI) at the start of each cycle (day 1) and the last day of cycle 6 (C6D28)
2. Serum Chemistry (Appendix VI), including Creatinine, bilirubin, ALT or AST at the start of each cycle (day 1)
3. Bone marrow aspirate and/or biopsy to confirm response, to be performed at the end of cycle 6. 10 ML of whole blood or bone marrow aspirate whichever available will be collected in extra lab tube. All bone marrows samples are to be stored at Cleveland Clinic
4. Conventional cytogenetics to be performed at the end of cycle 6
5. Documentation of frequency of transfusions (only PRBC and Platelets) prior to start of each new cycle.
6. Documentation in the medical record of any grade 2 or higher adverse events at each visit. For guidelines on SAE Reporting and AE entry for Case Report
7. Documentation of any prior administration of growth factors and ESA prior to start of each cycle
8. A 10 ML blood sample that will be used for next generation targeted deep sequencing of genes that are common in myeloid malignancies

9. Physical exam and ECOG performance status occurring at the end of each cycle
10. Vital signs occulting at each visit
11. Pregnancy test if applicable
12. MDS Response Assessment, assessed by the treating physician occurring at the end of cycle 6 or EOT, whichever occurs first.
13. Methylation panel only occurring in Cycle 1
14. Azacitidine will be administered intravenously or subcutaneously at a fixed dose of 75mg/m^2/day for 7 consecutive days, (allowing interruptions for weekends, and holidays, of each 28-day cycle).
15. Ascorbic acid will be administered orally daily at 1 g/day three days prior to start azacitidine and then continues daily for a total of 28 days of each 28 days cycle.

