## 11.2 Calendar

Period	Screening Period (Day-17 to Day -3)	Treatment Period														Extended Treatment Period Cycles	End Of Treatment (EOT)	Follow up k
		Cycle 1				Cycle 2		Cycle 3		Cycle 4		Cycle 5		Cycle 6				
Day		-3	1	7 c	14 n	1	7 c	28 g	1	7 c								
Administration of Azacitidine			X	X b		X	X b		X	X b								
Ascorbic Acid Dispensement		X a				X		X		X		X			X			
disease history and prior therapies	X																	
Record RBC/ platelets transfusion	X	X				X		X		X		X		X	X	X		
History and physical exam dm	X	X				X		X		X		X		X	X			X j
Vital signs d	X	X	X	X		X	X	X	X	X	X	X	X	X	X	X		X j
ECOG performance status em	X	X				X		X		X		X		X	X			X
Hematology dm	X	X				X	X	X	X	X	X	X	X	X	X	X		X j
Serum Chemistry d m	X	X				X		X		X		X		X	X			X
Pregnancy test	X														X			
Disease response assessment f	X														X	X		X
Bone marrow biopsy and aspiration L	X														X h			X i
Mutational analysis blood draw L	X l														X			
Methylation profile blood draw L	X		X	X	X													
Drug Diary Accountability		X				X		X		X		X		X	X	X		
Survival Follow up																		X k
Record adverse events m			↔ X →															

- A: For Cycle 1 only, patient will begin treatment with Ascorbic Acid 3 days prior to initial treatment of Azacitidine
- B: Azacitidine administration has a +/- 3 day window to account for breaks in treatment for weekends, and holidays
- C: Day 7 has a +/- 3 day window to account for breaks in treatment for weekends, holidays, and institutional standards
- D: See Appendix VI for required tests
- E: See Appendix I for performance status grading
- F: See Section for 12.0 for MDS/AML response assessment criteria
- G: If patient is eligible for the extended treatment period, and moving forward on the next cycle without a dosing delay, the C6D28 visit can serve as the visit of C7D1. If the patient is not eligible for the extended treatment period the patient's C6D28 visit can serve as the EOT visit.
- H: The cycle 6 bone marrow biopsy can occur up to 14 days (C6D14) prior to the C6D28 visit.
- I: EOT bone marrow biopsy is optional per discretion of the treating physician

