## **12.0 MEASUREMENT OF EFFECT**

The response criteria recommended by the MDS International Working Group 2006. Responses must be verified, documented, and signed at cycle 6 in the local medical record by the local PI. (Patients are considered non evaluable if they have received less than 2 courses of treatment, unless there is clear disease progression.)

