#### **APPENDIX IV: STUDY DESIGN TIME POINT DEFINITIONS**

Study Time Points	Definitions
Screening	Screening will occur from the time of the consent until day -4
Baseline/Enrollment	Days -17 b to Day -3 c
Treatment Period	Day 1 c to C6D28 or patient meets end of treatment criteria before completing 6 cycles
Extended Treatment Period (ETP)	The extended treatment period is defined as C7D1 to the patient meets EOT criteria
Study Treatment	The treatment period and if applicable the extended treatment period
End of Treatment (EOT)	The day patient meets the defined EOT criteria (Table 1) and discontinues study treatment.
Follow up	Patient will be followed bimonthly (60 days +/- 7 days) for a duration of 1 year after study
End of Study (EOS)	The time the patient completes 1 year of survival follow up and/or patient's death, whichever were to occur first.

A: Day 1 is defined as first dose of Azacitidine  
B: Day -17 is defined as 14 days prior to first dose of study Drug (Day -3)  
C: Day -3 is defined as day of Study Drug

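### Response duration is timed from the start of treatment, so it is a time to progression and includes each responder's time before response

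*Combined protocol and SAP*

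**What the plan says.** Section 14.0 gives the only operational definition: "Response duration to the combination recorded from start of treatment to progression". Section 2.2 and the Protocol Summary merely name the endpoint; section 2.2 has "The response duration for study patients", with no restriction to responders. The analysis plan in section 14.0 calls for descriptive statistics and names Kaplan-Meier only for overall survival.

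Four other places bear on the two ends of the interval:

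- **Start of treatment.** Section 3.2 says "The treatment period is defined as the time between first day of study drug dosage (Day - 3) to C6D28". The treatment-period row of Appendix IV begins at Day 1, and a footnote there says "Day 1 is defined as first dose of Azacitidine".
- **When response is established.** Section 12.0 says "Responses must be verified, documented, and signed at cycle 6 in the local medical record by the local PI". Section 11.1 schedules one on-treatment marrow, at the end of cycle 6, and the Calendar adds that "The cycle 6 bone marrow biopsy can occur up to 14 days (C6D14) prior to the C6D28 visit".
- **Hematologic improvement.** Section 12.0 requires it to last at least 8 weeks. Section 11.1 schedules "Hematology exams (Appendix VI) at the start of each cycle (day 1) and the last day of cycle 6 (C6D28").
- **Progression.** Table 1 in section 6.4 has "Disease progression defined as no response after 6 months of treatment or loss of response during treatment as defined in section 12". Section 12.0 defines relapse only after hematologic improvement.

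**The concern.** A duration of response should begin when the response begins. Timed from the first dose, the interval mixes how long a patient took to respond with how long the response held, and a slow responder is credited with extra durability. In this trial the marrow evidence for response comes late, so the time before response can be a material part of the reported figure.

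The definition also leaves open who is counted. Section 2.2 refers to study patients, and Table 1 treats absence of response after 6 months as progression. Taken literally, a patient who never responded could therefore be given a response duration of about 6 months.

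What is at stake is the meaning of one descriptive result. Anyone who reads the published figure as time in response would be misled about durability.

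**Working it through.** The plan gives no figure for response duration, and no sample size or power rests on it, so there is nothing to reproduce. The check is calendar arithmetic on the undelayed schedule.

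**Inputs**
- Cycles last 28 days (section 3.0).
- The diary in Appendix II runs -3, -2, -1, 1, with no Day 0, so Cycle 1 Day 1 is 3 elapsed days after Day -3.
- The cycle-6 marrow falls between C6D14 and C6D28 (section 11.1; Calendar footnote H).
- Blood counts are taken on day 1 of each cycle (section 11.1).
- One month is taken as 30.44 days.

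**Formula.** Elapsed days from Day -3 to cycle c, day d = 3 + 28(c - 1) + (d - 1). Subtract 3 to count from Day 1.

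**Response first documented by the cycle-6 marrow**
- C6D14: 3 + 140 + 13 = 156 days; 156 / 30.44 = 5.1 months.
- C6D28: 3 + 140 + 27 = 170 days; 170 / 30.44 = 5.6 months.
- From Day 1: 153 and 167 days, or 5.0 and 5.5 months.

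These are times to documentation. With no earlier scheduled marrow, onset may have come sooner, so they are upper bounds on the time before onset.

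**Hematologic improvement first met at a day-1 count**
- C2D1: 3 + 28 = 31 days (1.0 month).
- C3D1: 3 + 56 = 59 days (1.9 months).
- C4D1: 3 + 84 = 87 days (2.9 months).

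Whether C5D1 can qualify is not settled. It falls at 3 + 112 = 115 days, and 170 - 115 = 55 elapsed days remain to C6D28. That is one day short of 8 weeks, or exactly 56 days if both end days are counted. The documents do not say when the 8 weeks must be complete, so no firm later limit can be given.

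**Sensitivity to delay.** Section 7.0 allows up to 4 weeks' prolongation between cycles after the first two. Four such delays, before cycles 3 to 6, add 4 x 28 = 112 days. The marrow-documented range then becomes 268 to 282 days, or 8.8 to 9.3 months from Day -3.

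**End of the interval.** The overall survival definition in the same list names death and last follow-up; the response-duration definition names neither. Table 1 sends the reader to section 12.0 for loss of response. Section 12.0 gives a relapse rule after hematologic improvement, but none after complete or partial response in MDS and none for any AML response.

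**The case against.** The strongest reply is that this is a labelling matter. The start point is printed openly, the endpoint is descriptive, it enters no test or stopping rule, and the only planned external comparison is of overall survival. All of that is true and limits the consequence. It does not make the label match the quantity.

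A reader might infer that every responder's duration is inflated by more than 5 months, or that a 6-month response would appear nearly twice as long. The documents do not support that. The cycle-6 marrow date is when response is scheduled to be documented, not when it began. Percentages built on it treat the documentation date as the true start and so exaggerate. A patient with earlier hematologic improvement may be datable from blood counts. Section 11.1 also places the response assessment at end of treatment if that precedes cycle 6.

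A reader might also infer that non-responders will be included. Section 14.0 does not say so. The 6-month item in Table 1 is written as an end-of-treatment criterion, and a patient without a response would ordinarily not be timed. The point is only that nothing in the text excludes it.

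Two further gaps are minor. Silence on death would often be read as censoring at death; the rule needs stating, but either convention can be defended. The Day -3 versus Day 1 question is worth 3 days (0.1 month), and the marker on the Appendix IV row leads to the note on Day -3, so it may be no more than a slip.

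**Conclusion.** The point stands. As written, response duration is a time to progression, and each responder's value includes the time before response. On an undelayed schedule the addition is at most about 5.1 to 5.6 months from Day -3 (5.0 to 5.5 from Day 1) for a response first documented by the cycle-6 marrow. It is less for hematologic improvement dated by blood counts. The mean or median overstatement cannot be given, because the documents contain no distribution of time to response.

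The definitional finding rests on the current text alone. The sizes rest on 28-day cycles without delay and on the scheduled assessment dates. The primary response test and the two-stage rule use counts of responders and are untouched. This should be corrected before results are reported, but it does not threaten the trial's main conclusion.

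**What to change.** Rewrite the definition in section 14.0 so that response duration:

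- is measured in responders only;
- runs from the date of response to relapse or progression;
- states how death without progression is handled;
- censors patients alive without progression at the last disease assessment;
- is summarised by Kaplan-Meier.

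The analysis set and start date must agree. Either:

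1. include every patient who meets a response criterion at any time on treatment, including those who lose it before cycle 6, dated from when it is first met; or
2. limit the set to responders at the cycle-6 assessment and date from that assessment.

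Mixing the two would create a new bias. Requiring response at C6D28 while starting the clock at C2D1 guarantees 170 - 31 = 139 days. Under option 1, the 8-week requirement still gives every hematologic improvement at least 56 days, which should be acknowledged when the result is reported.

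State that the Table 1 item on no response after 6 months is not an event for this endpoint; its use for treatment decisions is a separate matter. The sponsor should reconcile Table 1 with section 12.0, since the relapse criteria it relies on exist only for hematologic improvement. If the interval from treatment start is wanted, report it separately as time to progression in all treated patients, with Day -3 or Day 1 named as origin.

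The cost is wording, plus relapse criteria to be cited or added. No new visits are needed: counts, transfusion records and the marrow date are already collected. There are three downsides. Reported durations will be shorter. Dating from a single cycle-6 marrow can understate duration when response began earlier. Some responders will be censored at end of treatment, because section 11.1 lists no marrow in the extended period, the end-of-treatment marrow is optional, and later follow-up is mainly for survival.
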